Our long-term research objective of this translational study is to establish a novel thrombus body scan (TBS) using a new fibrin-specific probe for positron emission tomography (PET) imaging to overcome the limitations of indirect VTE diagnosis, and, with one single test, provide a total-body assessment of fresh intravascular clot.

Scheme 1. Simplified synthetic route and chemical structure of ^{64}Cu -FBP8. The sequence of the core fibrin-binding peptide is reported on the bottom.

II. SPECIFIC AIMS

This proposal aims to generate strong evidence for VTE diagnosis using the thrombus body scan (TBS) from an initial small translational study that will justify a larger clinical study to obtain clinical approval for the TBS. We hypothesize that TBS using our new PET fibrin probe that specifically binds to fresh polymerized fibrin clot (< 1 week old), can directly detect thrombus anywhere in the body similar to ^{18}F -FDG PET scans for cancer nodules, will have better diagnostic accuracy for deep venous thrombosis and pulmonary embolus (DVT-PE) compared to current imaging modalities, can quantify the total body burden of fresh clot and can be performed in patients with renal dysfunction. Before we can fully test this hypothesis in an appropriately-powered clinical study, we propose a proof-of-concept study in a smaller cohort of patients to test the following specific aims and hypotheses:

1. Compare the presence, location and extent of PE diagnosed with the PET ⁶⁴Cu-FBP8 probe to conventional imaging. *Hypothesis:* The PET fibrin probe will allow direct imaging of acute thrombi causing PE, which is currently only indirectly diagnosed by filling defects on CT-angiogram or mismatched perfusion defects on V-Q scans.

2. Compare the presence, location and extent of DVT diagnosed with the PET ⁶⁴Cu-FBP8 probe to conventional imaging. *Hypothesis:* The PET fibrin probe will allow direct imaging of acute thrombi causing DVT diagnosed indirectly by incompressibility and loss of flow on lower extremity venous Doppler ultrasound.

3. In addition to PE and lower extremity DVT, assess for upper extremity and pelvic clot and compare the extent of total body clot burden imaged with the ⁶⁴Cu-FBP8 probe to the plasma D-dimer level. *Hypothesis:* The PET fibrin probe will discover acute thrombi including areas not assessed by current imaging methods and the total clot burden will correlate with the plasma D-dimer.

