Successful execution of this study will lay the groundwork for a clinical trial to compare the efficacy of a clot-specific imaging modality (**thrombus body scan or TBS**) that has the potential to be more accurate for the diagnosis of VTE, better able to establish the total clot burden in the body with a single test and more widely applicable to patients with renal failure and lung disease.

III. SUBJECT SELECTION

A total of eighty (80) subjects will be recruited for this study, which will be performed at the Massachusetts General Hospital (MGH). All eighty (80) subjects will be studied with the same protocol: a single injection of ⁶⁴Cu-FBP8 and PET-CT imaging at least three hours after injection at four bed positions, which will provide the imaging data for fresh blood clot at the three locations covering all three specific aims.

Inclusion Criteria:

Each subject must meet the following criteria to be enrolled in the study:

- 18 years of age or older with a clinically significant pulmonary embolus (PE) confirmed by a filling defect in CT angiography (CTA), and
- Subjects must receive the radiotracer injection within 72 hours of their diagnosis.

Exclusion Criteria:

- Subjects < 18 years of age
- Time of expected radiotracer injection > 72 hours from the time of a positive venous duplex ultrasound or CT-angiogram,
- Women subjects of childbearing potential who are pregnant, seeking to become pregnant, or have a positive serum pregnancy (beta-HCG) test,
- Unable to lie flat for 45 minutes as assessed by physical examination and medical history (e.g. back pain, arthritis, dyspnea),
- Weight that exceeds the PET camera table limit (300 kg)
- The subject will not be enrolled in the study if the radiation exposure for research studies during the prior 12 months, combined with the exposure from this study would exceed 50 mSv.
- Due to the radiation exposure from imaging studies, all women of childbearing potential will be required to have a negative serum pregnancy test performed prior to any imaging procedures on the same day (if not already done that day). Patients with a positive serum pregnancy test will be excluded. Breast feeding women will also be excluded.
- A pre-existing condition or use of a medication including vasopressors and tPA (due to its effects on clot) that in the opinion of the investigator may place the subject at a substantially increased risk
- Hemodynamic instability, including requiring escalating doses of vasopressor medication.

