- For subjects admitted to the hospital close to the scheduled time for imaging, which is at least 3 hours after injection, the subject will be escorted (transported) in the wheelchair or stretcher/bed by hospital transport and/or study staff depending on the subject conditions to the PET-CT suite; we will follow the hospital standard procedures for patient transport. The PET-CT technician will submit a patient transport order through Epic. When the PET suite becomes available, the hospital transport team will transport to the PET-CT location. If the subjects need to be monitored during the transport, then one of the study physicians will be present during the transport.
- Subjects coming as outpatient will come to the hospital (Anesthesia or Pulmonary Research area) at least 4 hours prior to the imaging where they will be injected and monitored before taking them to the PET-CT imaging suite.
- Prior to the scan subjects will be asked to urinate to minimize the possibility that they will need to move during the scan.
- The subjects will be positioned on the scanner table; support devices under the back and/or legs will be used as needed to enable the patient to comfortably maintain his/her position throughout the scan.
- A scout image (Topogram) which takes about 10 seconds will be obtained to locate the proper fields for imaging.
- Afterwards, CT and PET scans will be obtained for four bed positions: thorax, pelvis and thighs (2 positions). The CT scan for each position of the PET scans is necessary to correct for the attenuation of the ⁶⁴Cu-FBP8 activity caused by body tissue. We will perform an additional PET/CT scan of the lower portion of the thighs in order to image the full/whole thighs to the knees. Consequently, a total of 4 CT and 4 PET scans will be performed in four different positions. Imaging duration will be less than 10 seconds for each CT, and 10 minutes for each PET scan. The total time of imaging is expected to be approximately 45 minutes.
- We may have to repeat a PET-CT scan if we have an unexpected problem (for example, if subjects need to change position during a scan).
- Subjects will be monitored throughout the imaging session, and measurements including heart rate, blood pressure, and pulse oximetry will be recorded.

Post-scan procedures:

- After the scans are completed and last vital signs collected, the subject will be escorted back to his/her room on the ward if applicable

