Patients will be contacted at 3, 6 and 12 months following the diagnosis of PE. Death and recurrence of DVT-PE will be assessed. Results of any imaging studies (CT angiograms, echocardiograms, or venous duplex ultrasound studies) and serologic studies (follow up d-dimer) will be collected and patients will undergo a survey to collect information about symptoms attributable to PE-DVT as well as quality of life using Standard Form 36,²⁸ VEINES QOL29 and the patient's self-assessment of their overall health status on a 1 – 10 scale, with 1 indicating the worst possible and 10 the best possible health. For patients followed at MGH this will be done in person at the end of their PERT or pulmonary clinic follow up clinic visit. For those followed elsewhere, this will be done by telephone with subjects and their treating physicians. NYHA functional class, 6-min walk distance, and change in pulse oximetry with walking will be assessed.

VI. BIOSTATISTICAL ANALYSIS

Once a patient is enrolled, the subjects will receive an injection of up to 10 mCi ⁶⁴Cu-FBP8 and imaged with CT-PET approximately at least 3 hours after injection, when the “target-to-background” ratio (TBR) of activity is expected to be high based on previous studies.²⁷ With CT-PET the attenuation correction is done using a low-dose CT volumetric scan. Afterwards, PET acquisitions of 10 min duration each are performed in four positions, thorax, pelvis and thighs (2 positions), which are used to assess regional ⁶⁴Cu-FBP8 activity.

Specific data variables:

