The standardized uptake value (SUV) of ⁶⁴Cu-FBP8 uptake in the lungs, pelvis and thighs will be calculated. The target to background ratio (TBR) for ⁶⁴Cu-FBP8 activity will be calculated using as background a region of interest (ROI) created from large cardiac and vascular structures. This corrects the ⁶⁴Cu-FBP8 activity for differences in injected dose and timing of imaging and allows for flexibility in the image timing. One member of our group ([name]) and another from Nuclear Medicine ([name]) will be blinded to the clinical results and will identify the presence or absence of clot in the three imaged locations as well as the anatomic location(s) and extent as best as possible from the overlay of the fibrin activity on the attenuation correction CT scans. Additionally, we will perform quantitative image analyses including the volume of the thrombus ROI, activity of imaged clot in each imaged section and clot burden. The thrombus ROI is defined by a threshold of 50% between peak activity of the ROI and background activity. Multiple ROIs will be used in the case of separated thrombi. Clot burden will be estimated using the sum of ⁶⁴Cu-FBP8 activity within a thrombus ROI and then normalized by the injected dose.

Outcome Measures:

Specific Aim 1: The location and extent of the thrombus region of interest (ROI), its volume and clot burden within the lung ROI will be compared with the ROI of filling defects on CT-angiogram. We will determine the number and location of the thrombus ROI(s) within the lungs, and the overall clot burden as sum of ^{64}Cu -FBP8 activity within a thrombus ROI(s) within the lungs. Additionally, we will calculate the intersection of the thrombus ROI and filling defects ROI relative to volume of the thrombus ROI. That will quantify the fraction of thrombus ROI(s) using a scale from being are completely outside (0) to completely inside (1). Also, we will perform a lung segmentation using the software APOLLO (VIDA Diagnostics) and determine in which lung lobe the thrombus ROI(s) are located.

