Specific Aim 2: The thrombus ROI, its volume and clot burden within the thigh ROI will be compared with the location and extent of the clot on venous duplex ultrasound. We will determine the number and location of the thrombus ROI(s) within the thigh ROI, and the overall clot burden as sum of ^{64}Cu -FBP8 activity within a thrombus ROI(s) within the thigh ROI. Additionally, we will quantify the volumes and locations of the thrombus ROIs of the PET scan and the venous duplex ultrasound relative to each other. Also, we will perform a vessel segmentation using the 3D Slicer (open source software) and determine the location of thrombus ROI(s) with the blood vessel.

Specific Aim 3: The prevalence of high ^{64}Cu -FBP8 fibrin activity in the pelvic ROI and upper extremity ROI's will be reported. Additionally, as a secondary analysis, both the total fibrin activity in the imaged fields, excluding the liver, gallbladder, kidneys and urinary bladder normalized by injected dose for all patients will be correlated with the plasma D-dimer drawn at the time of imaging. D-dimer levels will be drawn daily from the time of first diagnostic imaging to the fibrin probe imaging (up to 3 days maximum in total) as well as PT, PTT, platelets and fibrinogen. Anticoagulants used, as well as timing and dose will be carefully recorded during this period.

For all Specific Aims, death, VTE recurrence, and quality of life measures will be compared with the clot burden measured by PET and conventional imaging modalities, stratified by treatment (systemic thrombolysis, catheter thrombolysis, or heparin alone) using multiple correlation, ANOVA, and t-tests for pairwise comparisons.

VII. RISKS AND DISCOMFORTS

^{64}Cu -FBP8 PET probe:

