Radiation exposure has been assessed for ^{64}Cu -FBP8 using human time-activity curves extrapolated from the time-dependent rat biodistribution data. The cumulative activity (Bq-h/Bq) for each source organ was determined by integrating the area under the time-activity curves by using the least-squares analysis, and organ absorbed doses were estimated by using the software program OLINDA/EXM (version 1.0, Vanderbilt University, 2003). Based on these data, the kidneys are the primary critical organs, followed by urinary bladder and liver. The estimated effective dose for humans was 0.017 mSv/MBq.²³ Initial data in human volunteers confirmed this effective dose estimate. We plan to inject no more than 370 MBq (=10 millicuries) per subject, which would cause a maximal effective dose of approximately 6.2 milliSieverts (mSv), and is less than the proposed up to 15 mCi in the original IND. The radiation exposure in this study will be small and there is no evidence that it represents a major health risk. If subjects have participated in other research studies in the past 12 months that have involved radiation exposure, they will be asked to inform the investigators or study staff (by placing a check mark on the consent form verifying that they have or have not been exposed to other radiation in the past 12 months). If it is determined that the prior radiation exposure exceeds our current guidelines (i.e. 50 mSv/year) the subject will not be enrolled in this study. We estimate that the total exposure of each subject to ionizing radiation includes:

1. Topogram 0.5 mSv (for identifying scanning region for CT)
2. Low-Resolution CT scans in four positions (thorax, pelvis and thigh x2): 0.95 mSv x 4 (for attenuation-correction of PET), which 3.8 mSv.
3. ^{64}Cu -FBP8 Injection (10 mCi x 0.62 mSv/mCi): 6.2 mSv

The estimated total radiation dose for a subject is 10.5 mSv. However, if we repeat a PET-CT scan for an unexpected problem (for example, if subjects need to change position during a scan), the total radiation dose for will be 11.45 mSv.

Discomfort

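### Aim 3 promises an upper-extremity prevalence, but the scan fields are thorax, pelvis and thighs, and neither the upper-extremity regions nor an evaluable denominator is defined

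*Combined protocol and SAP*

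**What the plan says.** All references are to the combined protocol and SAP.

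**What is promised.** Section II, Aim 3, sets out to "assess for upper extremity and pelvic clot and compare the extent of total body clot burden" with plasma D-dimer, and hypothesises that "the total clot burden will correlate with the plasma D-dimer". Section VI, Outcome Measures, Specific Aim 3, will report the prevalence of high "fibrin activity in the pelvic ROI and upper extremity" regions.

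**What is acquired.**
- Section III says the scan gives "imaging data for fresh blood clot at the three locations covering all three specific aims".
- Section V, PET-CT imaging: "CT and PET scans will be obtained for four bed positions: thorax, pelvis and thighs (2 positions".
- Section VI, opening paragraph: acquisitions are "performed in four positions, thorax, pelvis and thighs (2 positions), which are used to assess regional" tracer activity.
- Section VII, Radiation: "Low-Resolution CT scans in four positions (thorax, pelvis and thigh x2): 0.95 mSv x 4".

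**What is measured.** Under Specific data variables in Section VI, the SUV "uptake in the lungs, pelvis and thighs will be calculated". Two blinded readers call clot present or absent in the three scanned locations, and note its anatomic site and extent as far as they can. A 50% threshold between peak and background outlines each thrombus ROI. Clot burden is the summed activity inside thrombus ROIs, normalised by injected dose.

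**D-dimer.** The Aim 3 outcome describes a secondary correlation with D-dimer. The sentence opens with the word *both*, then names one quantity: total fibrin activity over the acquired fields, less four organs.

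**The concern.** The aim and its outcome name a body region that no description of the acquisition names. No section gives the position of the arms, says which upper-extremity veins must be visible, or asks for a record of whether they were evaluable in a given subject. The outcome mentions upper-extremity ROIs but does not define them.

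The plan also states no denominator. If the prevalence is taken over everyone scanned, a subject whose arm veins lay outside every field counts as negative. Few or no positives would then read as evidence that upper-extremity clot is rare, when part of the explanation is that it was not looked at. The study is meant to justify a larger trial of a total-body test, so such a figure could be carried forward.

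Two smaller gaps sit in the same outcome. *High* activity has no stated relation to the blinded call, which also leaves the pelvic prevalence open to interpretation. And the D-dimer sentence is incomplete, so the plan does not say whether the hypothesised quantity, clot burden, is the one correlated.

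**Working it through.** **1. Do the plan's own budgets contain an upper-extremity field?**

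Dose (Section VII, Radiation): topogram 0.5 mSv, CT 0.95 mSv for each of four named positions, tracer 6.2 mSv.

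0.5 + 4 × 0.95 + 6.2 = 0.5 + 3.8 + 6.2 = 10.5 mSv. This reproduces the stated total.

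The higher figure of 11.45 mSv equals 10.5 + 0.95, one more CT, and is reserved for repeating a scan after an unexpected problem.

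Time (Section V): four PET scans of 10 min are 40 min. Four CTs of under 10 s and a 10 s topogram add less than 1 min. The sum is about 41 min, consistent with the stated 45 min.

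Both budgets are accounted for by thorax, pelvis and two thigh positions. Neither includes a position for the upper extremity.

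**2. Promise against provision in Aim 3**

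| Element | Pelvis | Upper extremity |
|---|---|---|
| Own bed position | yes | no |
| SUV named | yes | no |
| Blinded present/absent call | yes | not as a named location |
| Region defined | by its field | named only |
| Evaluability recorded | not stated | not stated |
| Rule for *high* | not linked to the call | none |

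The 50% threshold does not fill the last row. It draws the edge of a thrombus ROI once one has been identified; it does not say when a region counts as positive.

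**3. What the denominator does**

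Inputs: 80 subjects (Section III). Evaluable numbers of 40 and 20 and the counts of positives are assumed, because the documents give none.

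With zero positives, the exact (Clopper-Pearson) two-sided 95% upper limit is 1 − 0.025^(1/n):
- n = 80: 1 − 0.025^(1/80) = 4.5%
- n = 40: 1 − 0.025^(1/40) = 8.8%
- n = 20: 1 − 0.025^(1/20) = 16.8%

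With four positives, using exact 95% intervals:
- 4/80 = 5.0% (1.4 to 12.3%)
- 4/40 = 10.0% (2.8 to 23.7%)
- 4/20 = 20.0% (5.7 to 43.7%)

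The same four positives are reported as anything from 5.0% to 20.0%, depending on a number the plan does not ask anyone to record.

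**4. D-dimer**

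The hypothesis concerns total clot burden, which Specific data variables defines inside thrombus ROIs. The one correlate named in the outcome is the signal over whole fields less four organs. These are different quantities, since the second is not confined to thrombus ROIs. The word *both* shows that a second correlate was intended, but the text does not identify it.

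**The case against.** The strongest reply is that arm veins may well be imaged. Proximal veins can lie in the thorax field, and arms at the side can lie in the pelvic or thigh fields. The readers note anatomic site, activity is to be measured in each imaged section, and separate thrombi get separate ROIs. So an upper-extremity clot could be recorded. This stands, and it rules out a stronger reading that a reader might infer: that the upper extremity is not imaged at all. The documents do not state arm position, so coverage is unspecified, not shown to be absent. But a clot that happens to be seen supplies a numerator only. A prevalence also needs to know in whom the segment could have been seen.

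Three other stronger readings are tempting and not supported:
- *The D-dimer analysis uses the wrong quantity.* The word *both* announces a second correlate, and clot burden is a natural candidate. The sentence is incomplete; it does not establish a substitution.
- *The pelvic prevalence cannot be obtained.* The pelvis has a bed position, an SUV and a blinded call. Only the link from *high* to that call is missing.
- *Aim 2 will count below-knee duplex clot as missed by PET because the PET field ends at the knees.* No section says that duplex examined below the knee.

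It is also fair to say that this is a proof-of-concept study and that the evaluable numbers above are invented. They show the direction and possible scale of the problem, not its size here.

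**Conclusion.** The point holds for the upper-extremity outcome. As written, the plan cannot give an interpretable upper-extremity prevalence, because the region is undefined, its coverage is unspecified and the number evaluable is not recorded. If the figure is taken over all 80 subjects, which is an assumption since no denominator is stated, zero positives would be reported with an upper limit of 4.5%. The limit would be 8.8% with 40 evaluable subjects or 16.8% with 20. The true evaluable number cannot be derived from the documents.

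The pelvic and D-dimer parts are clarifications: one missing link and one unfinished sentence. Aims 1 and 2 are not affected. This should be fixed, and confidence is high for the mismatch between outcome and fields.

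**What to change.** **(a) Upper extremity.** Choose one:
- Delete the upper-extremity wording from Aim 3 in Section II and from the Aim 3 outcome in Section VI.
- Restrict the outcome to named venous segments that lie inside any acquired field. Add those segments, and whether each is evaluable, to the existing blinded readers' task. Report prevalence over evaluable subjects only and state that number.

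**(b) *High* activity.** For the pelvis, and for the upper extremity if kept, base the prevalence on the existing blinded present/absent call. Otherwise state before reading how *high* relates to that call.

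**(c) D-dimer.** Complete the sentence in the Aim 3 outcome. State whether clot burden within thrombus ROIs, the quantity in the Aim 3 hypothesis, is the second correlate. Report any correlation with total activity under that name and not as a test of clot burden.

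**Cost.** Deletion, (b) and (c) need wording only. The restricted outcome adds a few items per subject to the reading form, narrows the claim, and gives a smaller denominator with a wider interval. No extra scan, dose or subject is needed.

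### Aim 3 hypothesises that clot burden correlates with D-dimer, but the only variable named for that correlation is a whole-field activity sum that keeps the plan's own background region, and a second announced variable is never named

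*Combined protocol and SAP*

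**What the plan says.** Section II, Aim 3, sets out to "compare the extent of total body clot burden imaged with the" probe against plasma D-dimer. Its hypothesis is that "the total clot burden will correlate with the plasma D-dimer".

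Section VI, Specific data variables, defines the terms. Clot burden is the sum of "activity within a thrombus ROI and then normalized by the injected dose". On segmentation: "The thrombus ROI is defined by a threshold of 50% between peak activity of the ROI and background activity", and "Multiple ROIs will be used in the case of separated thrombi". The target-to-background ratio (TBR) is calculated "using as background a region of interest (ROI) created from large cardiac and vascular structures".

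Section VI, Outcome Measures, Specific Aim 3, then plans the D-dimer correlation. The variable is introduced with the words "as a secondary analysis, both the total fibrin activity in the imaged fields, excluding the liver, gallbladder, kidneys and urinary bladder". It is divided by injected dose and correlated with the D-dimer taken at imaging. No second variable follows the word *both*.

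**The concern.** The hypothesis and the analysis use different quantities. Clot burden, as the plan defines it, is confined to thrombus ROIs. The variable named for the D-dimer correlation is everything in the imaged fields apart from four organs. That sum includes the blood pool from which the plan takes its background, and any other tissue not on the exclusion list.

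Two things are at stake. First, interpretation: a weak or null correlation with the whole-field sum could not be read as evidence that clot burden and D-dimer are unrelated, and a positive one could partly reflect non-clot activity. Second, pre-specification: with one of two announced variables unnamed, the correlate that tests the hypothesis can be chosen after the results are known.

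**Working it through.** The plan gives no target correlation, power or sample-size figure for this analysis, so there is no stated figure to reproduce. The check sets the texts side by side and then works out the direction of effect.

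**1. Which quantity appears where**

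| Place | Quantity set against D-dimer, or defined |
|---|---|
| Section II, Aim 3 statement | Total body clot burden |
| Section II, Aim 3 hypothesis | Total clot burden |
| Section VI, Specific data variables | Clot burden = thrombus-ROI activity ÷ injected dose |
| Section VI, Outcome Measures, Aim 3 | (Field activity − four organs) ÷ injected dose; second item after *both* absent |

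Variables announced: 2. Named: 1. Named and equal to the defined clot burden: 0.

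**2. Use of the term in the Outcome Measures.** Clot burden appears 2 times under Aim 1, 2 times under Aim 2, once in the paragraph covering all aims, and 0 times under Aim 3. The all-aims paragraph relates clot burden to mortality, recurrence and quality of life, not to D-dimer, so it does not fill the gap.

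**3. What the sum retains.** The thorax is one of the four bed positions, so the heart and great vessels are in the field. Excluded organs: 4. Excluded organs that belong to the cardiac and vascular background region: 0. Adding vessels to the exclusions would not repair the sum, because the clot lies in vessels.

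**4. Direction of effect.** Write the field sum as S = C + B, where C is clot activity and B is retained non-clot activity, both divided by injected dose, and let D be D-dimer. Then cov(S, D) = cov(C, D) + cov(B, D).

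- If B is independent of C and D, corr(S, D) = corr(C, D) ÷ √(1 + k), with k = var(B) ÷ var(C). The correlation shrinks for any k > 0.
- If B is related to D, the second covariance term is not zero and the bias can go either way. Such a link is plausible by inference: the probe is cleared by the kidneys, only eGFR below 30 is excluded, and Section I says that older patients have both more renal dysfunction and a less discriminating D-dimer. The documents do not quantify this.

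**5. Size.** The value of k is unknown. The documents give no human clot volume, no TBR value and no spread of background activity. Section VI expects a high TBR at imaging time, which would reduce the loss. But TBR is a contrast ratio, and the share of a field sum that comes from clot also depends on clot and tissue volumes. No figure is offered.

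**The case against.** The strongest reply has four parts.

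- **The two complaints compete.** If the lost second item is ROI clot burden, the hypothesis is tested as defined and only a drafting slip remains. If *both* is a stray word, there is no hidden choice. This is fair: the documents do not say which reading is right. But each reading leaves a defect. Under the first, the variable that tests the hypothesis is not written down. Under the second, the hypothesis has no direct test.
- **Fibrin activity might mean signal already read as clot.** This is strained. The sum is defined by imaged fields with whole organs removed, the plan uses the phrase for probe signal generally, and clot burden has its own defined term.
- **ROI burden is not clearly the better measure.** The 50% threshold may omit low-uptake or diffuse clot, segmentation error also shrinks a correlation, and no background subtraction is described inside the ROI. All of this stands, and no claim is made about which loss is larger. ROI burden is preferred as the main variable because it is the quantity the hypothesis names and the plan defines. Aims 1 and 2 already depend on the same segmentation.
- **It is only a secondary analysis in a small study.** This stands and limits the severity. It is nevertheless the only stated test of the D-dimer half of a specific aim.

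**Conclusion.** The concern holds and should be fixed. The one variable written down for the D-dimer correlation is not the clot burden in the hypothesis, it keeps the region that the plan itself treats as background, and the second variable is missing. This rests on reading the Aim 3 variable literally as a whole-field sum less four organs, and on taking *both* to announce two items. Confidence is medium, because the intended second variable cannot be known from the text.

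The numerical effect on the correlation cannot be estimated. Non-clot activity unrelated to D-dimer weakens the correlation; related activity could bias it in either direction. The prevalence part of Aim 3 and the Aim 1 and Aim 2 analyses are not affected.

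**What to change.** In Section VI, Outcome Measures, Specific Aim 3, replace *both* with two named variables and state which one tests the hypothesis:

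1. **Main:** clot burden as defined under Specific data variables, that is, activity summed over all thrombus ROIs in the thorax, pelvis and thigh fields, divided by injected dose, and correlated with the D-dimer drawn at the time of imaging.
2. **Sensitivity analysis, labelled as such:** the whole-field sum less the four organs, divided by injected dose, as now written.

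If a different second variable was intended, name it before the data are analysed.

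The cost is one or two sentences and one extra sum. Section VI already plans the "activity of imaged clot in each imaged section and clot burden", and D-dimer is drawn in any case, so no new data or procedures are needed. The downside is reliance on ROI segmentation and its 50% threshold. Keeping the whole-field sum as a sensitivity analysis covers clot that the threshold might miss.
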